8.1.4 Physical Examination

A complete physical examination will be performed by either the investigator or a sub-investigator who is a physician at the screening visit and visit numbers 2-7. Qualified staff (MD, NP, RN, and PA) may complete the abbreviated physical exam at all other visits. New abnormal physical exam findings must be documented and will be followed by a physician or other qualified staff at the next scheduled visit.

8.1.5 Vital Signs

Body temperature, blood pressure, pulse and respirations will be performed after resting for 5 minutes will be performed as needed and during physical examinations.

8.1.6 Standardized X-rays

45° flexion standing weight-bearing, lateral and merchant views x-rays should be completed at or before screening visit

8.1.7 Functional Testing

12-minute walk test, gait analysis, and 3-day accelerometer test will be completed during the screening visit. The walk test involves simple physical movements such as walking and the accelerometer is worn by the patient prior to the visit to measure activity levels. The 12-minute walk test and 3-day accelerometer test will be administered again during their 6 month, 18 month, 24 month, 30 month, and 36 month visits.

8.1.8 Administration of Injection

Using an 18- to 22-gauge needle, the doctor will remove synovial fluid or effusion before each SYNVISC (hylan g-f 20) (2ml) injection. Using an 18- to 22-gauge needle, the doctor will inject the full 2 mL in one knee only.

8.1.10 Concomitant Medication Review

Patient will be asked about any medications they are taking. Current treatments and medications will be documented during each patient encounter.

8.1.11 Email or phone contact

A member of the research team will contact the subjects every 6 weeks, either by email or phone, to assess for pain, other treatment history and any adverse events.

8.1.12 Questionnaires and Assessments

Patients will either complete on their own or be asked questions from the WOMAC, Lysholm-Tegner, Worst Knee Pain, KOOS, and SF-12 assessments by their doctor or another study staff member who will record the appropriate scores during the screening visit. Patients will be assessed again with the Worst Knee Pain, KOOS, SF-12 and WOMAC assessments during their 6month, 18 month, 24 month, 30month, and 36month visits.

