| SAFETY EVALUATIONS | 
The repeat treatment phase evaluated the safety profile of a second injection of Synvisc-One. One hundred and sixty patients were treated during this phase of the study, of which 77 patients received a second injection of Synvisc-One. These patients were followed for 4 weeks and out of 77 patients, only 4 (5.2%) experienced device-related AEs in the injected knee. All such events were mild to moderate and were treated symptomatically. Patients who developed injected knee AEs during the initial phase of the study, and who subsequently received repeat treatment, did not experience injected knee AEs upon repeat exposure to Synvisc-One.
 |
| PLANNED INTERIM ANALYSES | 
There is no interim analysis planned. Serious adverse events will be monitored by the committee on an ongoing basis throughout the study.
 |

| | |
|---|---|
| 
STATISTICS Primary Analysis Endpoint
 | 
The primary endpoint for the study will be analyzed using a responder analysis. The proportion of responders following injection within the 6 months following the baseline injection will be calculated based on Worst Knee Pain scores ≤ 3 on a 0-10 pain scale, which is a threshold consistent with other similar studies (Tubach 2005, Bellamy 2010). The primary endpoint is defined as non-inferiority of the proportion of responders in our study relative to an external criterion for the responder proportion (Bellamy 2010). Bellamy demonstrated in his paper from 2007 (table 3) that a BLISS response at any time during the study was achieved in 70% receiving appropriate care and Hylan G-F 20 and only in 38% of patients receiving appropriate care ($P < 0.0001$). We propose a non-inferiority delta of 20% relative to this external criterion, and thus the primary endpoint will be tested by a test of our sample proportion (p) with null hypothesis $H_0: p < 0.50$ vs. alternative hypothesis $H_1: p \geq 0.50$. This test will be performed using the Wilson-Agresti method for testing a single binomial proportion at a one-sided significance level of 0.025 (i.e. non-inferiority will be satisfied if the 95% Wilson-Agresti (REF BROWN ET AL 2001) interval for the proportion of responders excludes the null rate of 0.50).
 |

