5.2 Inclusion Criteria

Inclusion Criteria:

1. Male or female patients aged 30-50 years
2. History of symptomatic unilateral primary or secondary knee OA for more than 6 months

3. Signed written informed consent
 4. Radiographic evidence of Kellgren-Lawrence Grade I or II OA of the target knee
 5. Body Mass Index (BMI) < 30 kg/m²
 6. Activity criteria (Tegner score > 3)
 7. Continued target knee OA pain despite conservative treatment \geq 3 months (e.g., weight reduction, physical therapy, analgesics)
 8. Willing to withhold intake of NSAIDs (including COX-2 inhibitors) and analgesics, for a washout period of minimum 3 days up to 21 days prior to baseline visit (depending on medication)
 9. Willing to discontinue prohibited treatments and medications throughout study period
- Baseline inclusion criteria
10. Completed OA medication washout period
 11. Target knee pain 4-8 (0-10 NRS) during most painful knee movement (Worst Knee Pain)
 12. If female, must have had a negative urine pregnancy test and used a medically acceptable form of contraception for at least 1 month prior to baseline and agree to continued use of contraception for the duration of the study. Otherwise, females must be surgically sterile, or postmenopausal (as documented in medical history) for at least 1 year. The fetal safety profile for G-F 20 is unknown. Pregnancy will affect the individual's regular activity levels. Females who become pregnant during the study will be excluded from the study. Subjects who become pregnant will be followed up by telephone every 3 months to check for any adverse effects. They will also be recommended to follow routine obstetric visits. Males should be able to father children as it has no expected effects on activity levels.

5.3 Exclusion Criteria:

1. Known allergy to hylan G-F 20 or any of its components, or to avian proteins, eggs, feathers, down, or poultry
2. Clinically apparent tense effusion or other acute inflammation of the target knee at baseline
3. History of target knee viscosupplementation treatment
4. History of major surgery for OA in target knee including arthroplasty or tibial osteotomy
5. Arthroscopic surgery or intra-articular steroid injection in target knee within six months of baseline visit
6. Significant (as judged by the Investigator) alignment deformity of target knee
7. Ipsilateral symptomatic OA of hip or ankle; contralateral symptomatic OA of hip, knee, or ankle
8. History of:
9. Septic OA of any joint

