7.4.2 Dispensing

The Synvisc-One devices will be couriered to the Orthopaedic Institute by the UCSF investigational pharmacy according to subject enrollment by a pharmacy staff member. Upon device transfer from the pharmacy, the investigator shall maintain the devices at controlled room temperature in a designated area in a locked cabinet until they are released for patient administration upon the order of the investigator. The study investigators will administer the injections.

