13 STATISTICAL METHODS AND CONSIDERATIONS

Prior to the analysis of the final study data, a detailed Statistical Analysis Plan (SAP) will be written describing all analyses that will be performed. The SAP will contain any modifications to the analysis plan described below.

Data Sets Analyzed

The primary endpoint is based on a responder analysis. Response is defined as maintaining a Worst Knee Pain score ≤ 3 on a 0-10 pain scale throughout the 6 months following the baseline injection. Trial success will be based on a non-inferiority test (with 20% non-inferiority threshold) of this response rate in comparison to an external criterion of 70% (Bellamy 2010). Secondary endpoints include determining the duration of response after subsequent injection, determining the effects of treatment on activity levels and quality of life, and describing the three-year time course of each of the study endpoints. The sample size will be $n=150$ subjects followed for up to 3 years after baseline injection. The power to conclude non-inferiority for a true response rate of 65% is better than 92%.

Demographic and Baseline Characteristics

The following demographic variables at screening will be summarized by: race, gender, age, height and weight.

Analysis of Primary Endpoint

The primary endpoint for the study will be analyzed using a responder analysis. The proportion of responders following injection within the 6 months following the baseline injection will be calculated based on Worst Knee Pain scores ≤ 3 on a 0-10 pain scale, which is a threshold consistent with other similar studies (Tubach 2005, Bellamy 2010). The primary endpoint is defined as non-inferiority (with 20% non-inferiority threshold) of the proportion of responders in our study relative to an external criterion of 70% for the responder proportion (Bellamy 2010).

Primary Statistical Analysis: Define the true probability of a subject being a responder as π and the non-inferiority threshold $\delta_{NI} = 0.20$. We require the test of

$$H_0: \pi < 0.70 - \delta_{NI} = 0.50$$

vs. the alternative

$$H_1: \pi \geq 0.70 - \delta_{NI} = 0.50.$$

Non-inferiority will be accepted if the null hypothesis can be rejected with a 2.5% one-sided type I error. To test this hypothesis, we will use the Wilson-Agresti method for a single binomial proportion. Non inferiority will be accepted if the 95% Wilson-Agresti (REF BROWN ET AL 2001) interval for the proportion of responders excludes the null rate of 0.50.

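### Neither the mode nor the rater of the Worst Knee Pain score is fixed: a doctor may record it at screening, and the response ratings have no stated safeguard in an open-label, single-arm trial

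*Combined protocol and SAP*

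**What the plan says.** **Entry.** Section 5.2 requires "Target knee pain 4-8 (0-10 NRS) during most painful knee movement (Worst Knee Pain"). Appendix 1 schedules this score at screening and at every visit from 6 months on.

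**Response.** Section 13 defines a response by the same item at 3 or less. Its Data Sets Analyzed paragraph requires the score to be maintained throughout the 6 months after the baseline injection. Its Analysis of Primary Endpoint paragraph and the Synopsis speak only of responders within those 6 months.

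**Who asks and records.**
- Screening (8.1.12): patients complete the instruments themselves or may "be asked questions from the WOMAC, Lysholm-Tegner, Worst Knee Pain, KOOS, and SF-12 assessments by their doctor or another study staff member". The sentence goes on to say that this person records the scores, and ties this to the screening visit.
- Weeks 6, 12 and 18 (8.1.11 and Section 9): a research team member makes contact "either by email or phone, to assess for pain, other treatment history and any adverse events". Section 9 lists Worst Knee Pain among the items collected.
- The 6-month visit (8.1.12): patients are assessed again, with no mode or rater named.

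**Setting.** Section 3.1 describes an open-label cohort, 7.2 dispenses with blinding, and 7.3 provides no control product. Section 7.4.2 states: "The study investigators will administer the injections".

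**Decision rule.** The test is "at a one-sided significance level of 0.025" (Synopsis, primary analysis). Non-inferiority is accepted if the 95% Wilson-Agresti "interval for the proportion of responders excludes the null rate of 0.50" (Section 13).

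**The concern.** Worst Knee Pain is a patient-reported 0-10 rating, and such ratings can depend on who asks and how. The lowest eligible score is 4 and the highest responding score is 3, so the two cuts are adjacent integers on one item. A true 3 recorded as 4 at screening admits a patient who already meets the response threshold. A true 4 recorded as 3 at follow-up can create or preserve a response.

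The mode can differ between a subject's screening and follow-up ratings, and between contacts within the 6-month window. Everyone who might ask knows that the patient was injected, and nothing in the visible text keeps the injector from asking at the 6-month visit.

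In a randomised comparison, effects of this kind would act on both arms and largely cancel. Here the comparison is with a fixed number, so any systematic shift enters the observed response rate in full.

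**Working it through.** **1. Inputs from the plan.** The reference rate comes from "relative to an external criterion of 70% for the responder proportion" and the margin from "We propose a non-inferiority delta of 20% relative to this external criterion", so the null rate is 0.70 − 0.20 = 0.50. Planned n = 150, or n = 120 after 20% dropout (Synopsis, sample size). One-sided alpha is 0.025.

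**2. Success count.** With p = x/n and z = 1.96, the Wilson lower limit is

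L = [p + z²/(2n) − z·√(p(1−p)/n + z²/(4n²))] / (1 + z²/n).

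- n = 150: L(87) = 0.49998 and L(88) = 0.5067, so 88 responders are needed, 13 above half.
- n = 120: L(70) = 0.4939 and L(71) = 0.5022, so 71 are needed, 11 above half.

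The Agresti-Coull form gives the same counts.

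**3. The plan's power table.** Power is the exact binomial tail P(X ≥ r | n, p).

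| n | r | true rate 0.60 | true rate 0.65 | plan states |
|---|---|---|---|---|
| 120 | 71 | 61.2% | 92.3% | 61% / 92% |
| 150 | 87 | 72.1% | 96.9% | 72% / 97% |
| 150 | 88 | 66.3% | 95.5% | 72% / 97% |

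The n = 120 column reproduces. The n = 150 column reproduces only with 87, where the lower limit reaches 0.50 only by rounding. The strict count of 88 is used below.

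**4. Generic sensitivity check.** Let s be the net share of all subjects moved from non-response to response. The observed rate is then 0.50 + s. The values of s are assumptions; the documents give no rater or mode effect.

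| s | subjects of 150 | observed rate | P(success), n = 150 | P(success), n = 120 |
|---|---|---|---|---|
| 0 | 0 | 0.500 | 2.0% | 2.7% |
| 1% | 1.5 | 0.510 | 3.6% | 4.4% |
| 2.5% | 3.75 | 0.525 | 7.6% | 8.5% |
| 5% | 7.5 | 0.550 | 20.6% | 20.5% |

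At a true rate of 0.50, half the subjects are non-responders, so s = 2.5% and 5% mean that 5% and 10% of true non-responders are reclassified.

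**5. Dependence on the true rate.** At a true rate of 0.45 and n = 150, reclassifying 5% of non-responders gives an observed rate of 0.45 + 0.55 × 0.05 = 0.4775 and a 0.5% chance of success. Reclassifying 10% gives 0.505 and 2.7%. The inflation matters mainly when the true rate is close to 0.50.

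**6. What this does not measure.** Bias of the same size from any source would give these numbers. They describe a shift at response. Drift at entry is the stage for which doctor recording is documented, and it cannot be quantified because the plan gives no distribution of screening scores.

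**The case against.** A reader might infer that the patient's own doctor records the response scores as well. The documents do not say so. The sentence in 8.1.12 that names the doctor is limited to the screening visit. Three of the four scheduled ratings in the 6-month window come by email or phone through a research team member who is not stated to be the doctor. For the 6-month visit, Section 9 lists Worst Knee Pain under a study questionnaire and the Synopsis speaks of a patient questionnaire. That leans towards patient completion without requiring it. This objection stands: doctor recording is documented for entry only.

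A reader might also infer that a one-point nudge generally makes a responder. Entry runs from 4 to 8, and only a subject who would otherwise score 4 at follow-up crosses by one point. If response must hold throughout the 6 months, the other ratings must qualify too. If one qualifying score within the window suffices, a single influenced rating is enough. Exposure thus depends on a definition that the plan leaves open, but neither reading removes it.

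The REDCap forms mentioned in Appendix II are not in the text available here, and they may fix the wording, recall period or mode. The point is therefore confined to the visible text.

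Finally, self-completion and email are already permitted, and patient expectation in an open-label study survives any change of rater. Both are true. They limit what the fix can achieve, but an avoidable source of variation would still be left in place.

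**Conclusion.** The point holds in a limited form. The entry score may be asked and recorded by the patient's doctor. The mode of the response ratings varies or is unstated, their rater at the 6-month visit is not fixed, and the visible text requires neither self-completion, nor a non-injecting rater, nor a record of the mode. With no control arm, any systematic effect adds directly to the rate tested against 0.50.

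Its size is unknown. The sensitivity figures rest on three assumptions: a true rate of exactly 0.50, a success count of 88 of 150, and net shifts chosen for illustration. On those terms a 2.5% shift more than triples the 2.0% chance of success and a 5% shift raises it about tenfold. They show how little movement the rule tolerates near its boundary. They are not evidence that rater influence of that size will occur. This is an inexpensive improvement to a stated procedure and does not by itself invalidate the design.

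**What to change.** Amend 8.1.11 and 8.1.12 so that every Worst Knee Pain rating (screening or baseline, weeks 6, 12 and 18, and each clinic visit) is completed by the patient with the same wording and recall period. Use a REDCap link for remote ratings, and a tablet or paper form at the clinic before the patient sees the investigator. Allow phone only as a fallback, read from a script by existing staff who did not inject. Record the mode of each rating. State that the treating doctor neither asks for nor records the score. If the Appendix II forms already fix wording and recall period, refer to them.

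The cost is small, because REDCap and email contact are already planned and no visit, entry cut or sample size changes. More reminders will be needed and a few more ratings may be missed. The Missing Data paragraph in Section 13 covers only patients who discontinue, so a rule for a single missed rating should be added at the same time. Expectation bias on the patient's side will remain and should be acknowledged when the result is reported.

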8.1.13 Adverse Events

Information regarding occurrence of adverse events will be captured throughout the study. Duration (start and stop dates and times), severity/grade, outcome, treatment and relation to study drug will be recorded on the case report form (CRF).

8.2 Clinical Laboratory Measurements

8.2.1 Pregnancy Test

A urine pregnancy test will be obtained from female subjects who are of childbearing age prior to their participation in the study.

 2. KOOS
 3. SF-12
 4. WOMAC

Visit 3 (12 months post injection)

- Physical examination
- Functional testing:
 1. 12-minute Walk test
 2. 3-day accelerometer test
- Evaluation instruments (study questionnaire):
 1. Worst Knee Pain
 2. KOOS
 3. SF-12
 4. WOMAC

Visit 4 (18 months post injection)

- Physical examination
- Functional testing:
 1. 12-minute Walk test
 2. 3-day accelerometer test
- Evaluation instruments (study questionnaire):
 1. Worst Knee Pain
 2. KOOS
 3. SF-12
 4. WOMAC

Visit 5 (24 months post injection)

- Physical examination
- Functional testing:
 1. 12-minute Walk test
 2. 3-day accelerometer test
- Evaluation instruments (study questionnaire):
 1. Worst Knee Pain

- 2. KOOS
- 3. SF-12
- 4. WOMAC
 - **Visit 6** (30 months post injection)
 - Physical examination
 - Functional testing:
 1. 12-minute Walk test
 2. 3-day accelerometer test
 - Evaluation instruments (study questionnaire):
 1. Worst Knee Pain
 2. KOOS
 3. SF-12
 4. WOMAC
 - **Visit 7** (36 months post injection)
 - Physical examination
 - Functional testing:
 1. 12-minute Walk test
 2. 3-day accelerometer test
 - Evaluation instruments (study questionnaire):
 1. Worst Knee Pain
 2. KOOS
 3. SF-12
 4. WOMAC

Email or phone contact at 6, 12 and 18 weeks post each injection and clinic visit to check for any changes in medical condition.

- Worst Knee Pain (0-10 NRS)
- Other treatment history
- Adverse events

| Office Visit | What you do |
|--|---|
| 1-3 weeks before starting study treatment | Physical exam X-ray Study questionnaire 12 minute walk test 3-day accelerometer test |
| Visit 1 - Baseline | Synvisc-One injection in the affected knee |

| | |
|--|---|
| 
Visit 2 – 6 months after injection Visit 3 – 1 year after injection Visit 4 – 1.5 years after injection Visit 5 – 2 years after injection Visit 6 – 2.5 years after injection
 
Email or phone contact at 6, 12 and 18 weeks after each injection and office visit
 | 
Physical exam Study questionnaire 12 minute walk test 3-day accelerometer test
 
Check up on your medical condition
 |
|--|---|

10 ADVERSE EXPERIENCE REPORTING AND DOCUMENTATION

ADVERSE EVENTS

An adverse event (AE) is any untoward medical occurrence in a clinical investigation of a patient administered a pharmaceutical product and that does not necessarily have a causal relationship with the treatment. An AE is therefore any unfavorable and unintended sign (including an abnormal laboratory finding), symptom or disease temporally associated with the administration of an investigational product, whether or not related to that investigational product. An unexpected AE is one of a type not identified in nature, severity, or frequency in the current Investigator’s Brochure or of greater severity or frequency than expected based on the information in the Investigator’s Brochure.

The Investigator will probe, via discussion with the subject, for the occurrence of AEs during each subject visit and record the information in the site’s source documents. Adverse events will be recorded in the patient CRF. Adverse events will be described by duration (start and stop dates and times), severity, outcome, treatment and relation to study drug, or if unrelated, the cause.

AE Severity

The National Cancer Institute’s Common Terminology Criteria for Adverse Events (CTCAE) Version 3.0 should be used to assess and grade AE severity, including laboratory abnormalities judged to be clinically significant. The modified criteria can be found in the study manual. If the experience is not covered in the modified criteria, the guidelines shown in Table 1 below should be used to grade severity. It should be pointed out that the term “severe” is a measure of intensity and that a severe AE is not necessarily serious.

Table 1. AE Severity Grading

| Severity (Toxicity Grade) | Description |
|----------------------------------|---|
| Mild (1) | Transient or mild discomfort; no limitation in activity; no medical intervention or therapy required. The subject may be aware of the sign or symptom but tolerates it reasonably well. |
| Moderate (2) | Mild to moderate limitation in activity, no or minimal medical intervention/therapy required. |
| Severe (3) | Marked limitation in activity, medical intervention/therapy required, hospitalizations possible. |
| Life-threatening (4) | The subject is at risk of death due to the adverse experience as it occurred. This does not refer to an experience that hypothetically might have caused death if it were more severe. |

AE Relationship to Study Drug

The relationship of an AE to Synvisc-One should be assessed using the following the guidelines in Table 2.

Table 2. AE Relationship to Study Drug

| Relationship to Drug | Comment |
|-----------------------------|---|
| Definitely | Previously known toxicity of agent; or an event that follows a reasonable temporal sequence from administration of the drug; that follows a known or expected response pattern to the suspected drug; that is confirmed by stopping or reducing the dosage of the drug; and that is not explained by any other reasonable hypothesis. |
| Probably | An event that follows a reasonable temporal sequence from administration of the drug; that follows a known or expected response pattern to the suspected drug; that is confirmed by stopping or reducing the dosage of the drug; and that is unlikely to be explained by the known characteristics of the subject's clinical state or by other interventions. |
| Possibly | An event that follows a reasonable temporal sequence from administration of the drug; that follows a known or expected response pattern to that suspected drug; but that could readily have been produced by a number of other factors. |
| Unrelated | An event that can be determined with certainty to have no relationship to the study drug. |

Serious Adverse Experiences (SAE)

An SAE is defined as any AE occurring at any dose that results in any of the following outcomes:

- death

- a life-threatening adverse experience
- inpatient hospitalization or prolongation of existing hospitalization
- a persistent or significant disability/incapacity
- a congenital anomaly/birth defect

Other important medical events may also be considered an SAE when, based on appropriate medical judgment, they jeopardize the subject or require intervention to prevent one of the outcomes listed.

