16.5 Investigator Responsibilities41

LIST OF ABBREVIATIONS

| | |
|--------------|---|
| AE | Adverse event |
| CFR | Code of Federal Regulations |
| CRF | Case report form |
| DMC | Data Monitoring Committee |
| DSMB | Data Safety Monitoring Board |
| FDA | Food and Drug Administration |
| GCP | Good Clinical Practice |
| HIPAA | Health Insurance Portability and Accountability Act of 1996 |
| ICF | Informed consent form |
| ICH | International Conference on Harmonization |
| IEC | Independent Ethics Committee |
| IRB | Institutional Review Board |
| PI | Principal Investigator |
| SAE | Serious adverse experience |
| NSAID | Non-steroidal anti-inflammatory drugs: also known as “NSAIDs”; medication used to treat pain or swelling. |
| OA | Osteoarthritis |

PROTOCOL SYNOPSIS

| | |
|-----------------------------|--|
| TITLE | Long-term Management of “Younger, Active” Patients with Pain from Early Knee Osteoarthritis with Synvisc-One (hylan G-F 20) |
| SPONSOR | [name], University of California San Francisco |
| FUNDING ORGANIZATION | Genzyme |
| NUMBER OF SITES | 1 |
| RATIONALE | 
The objectives of the study are to assess the effectiveness, duration of symptom relief, improvements on activity level and safety of one or more hylan G-F 20 injections for symptomatic early knee osteoarthritis (OA) treatment in younger, active patients over a three-year period.
 
 •From a pain management perspective, reduction of knee pain knee pain will target a Patient Acceptable Symptom State (PASS) •Repeated hylan G-F 20 treatment will be allowed as necessary to maintain patients in PASS throughout the duration of the study period. |

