4.3 Safety Evaluations

Adverse reactions will be checked on all phone interviews and clinic visits. Adverse reactions will be captured and tabulated

The most commonly reported related local adverse events were transient, mild-to-moderate arthralgia, arthritis, arthropathy, injection site pain and joint effusion. No serious adverse events were reported in clinical trials in knees injected with Synvisc-One. Serious local adverse events have been reported only rarely in post-marketing use. Repeat treatment did not affect the safety profile. In the pivotal clinical trial, there was one related systemic event of syncope. The most common systemic side effects irrespective of relationship to Synvisc-One were headache, back pain, nasopharyngitis and influenza. Systemic adverse event profiles were similar between patients in the Synvisc-One and Saline Control groups.

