10.1.1 Serious Adverse Experience Reporting

Study sites will document all SAEs that occur (whether or not related to study drug) per [UCSF CHR Guidelines](#). The collection period for all SAEs will begin after informed consent is obtained and end after procedures for the final study visit have been completed. Institution and Investigator understand and agree that Investigator and Institution are obligated under applicable law and regulations to report any serious and related adverse event, if any, that occurs during treatment with the Product to the Institution's IRB and to the governing regulatory authority in accordance with applicable filing timelines promptly after any such event occurs. Prior to or at the time of filing any such report with the governing regulatory authority, Investigator, within 24 hours of first knowledge of such serious and related adverse event, will also transmit an information copy of the report to Genzyme via fax, attention: Genzyme PV, [contact] or by e-mail to [contact]. In accordance with the standard operating procedures and policies of the local Institutional Review Board (IRB)/Independent Ethics Committee (IEC), the site investigator will report SAEs to the IRB/IEC.

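### Table 2 lets a knee event be graded Definitely related with no timing or alternative-cause condition, so the top causality grade is easier to reach than the grades below it

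*Combined protocol and SAP*

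**What the plan says.** Section 10 states that the relationship of an adverse event to Synvisc-One "should be assessed using the following the guidelines in Table 2". The table has four grades.

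- *Definitely* begins "Previously known toxicity of agent; or an event that follows a reasonable temporal sequence from administration of the drug". It goes on to an expected response pattern and then to an event "that is confirmed by stopping or reducing the dosage of the drug; and that is not explained by any other reasonable hypothesis".
- *Probably* asks for a reasonable temporal sequence, an expected pattern, confirmation by stopping or reducing the dose, and that the subject's clinical state or other interventions are unlikely to explain the event.
- *Possibly* asks for a reasonable temporal sequence and an expected pattern, "but that could readily have been produced by a number of other factors".
- *Unrelated* is "An event that can be determined with certainty to have no relationship to the study drug".

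Section 4.3 gives the known local reactions: "The most commonly reported related local adverse events were transient, mild-to-moderate arthralgia, arthritis, arthropathy, injection site pain and joint effusion". The Rationale in the Protocol Synopsis makes the "safety of one or more hylan G-F 20 injections for symptomatic early knee osteoarthritis (OA) treatment" part of the study's objectives. Section 10.1.1 requires a copy of the report to go to the funder "within 24 hours of first knowledge of such serious and related adverse event".

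**The concern.** A causality scale should demand more evidence as the grade rises. Here one route to the highest grade demands less than the two grades below it. That would matter little if the product's known toxicities were distinctive, but four of the five named in Section 4.3 are also ways in which knee OA shows itself. The protocol expects pain to recur (Section 2.1, Specific Aim 2), enrols active patients (Tegner score above 3, Section 5.2), and collects adverse events throughout the study (Section 8.1.13), with enquiries every 6 weeks (Section 8.1.11).

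There is no control product (Section 7.3), so the investigator's grade is the main planned means of separating reactions to the injection from the course of the disease. If two investigators can read the table correctly and give the same late effusion the highest grade and a low one, the tabulation by relationship cannot be reproduced.

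**Working it through.** No calculation applies to the wording itself, so the check sets the rows side by side.

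| Route | Timing | Expected pattern | Confirmed by stopping or reducing dose | Other causes |
|---|---|---|---|---|
| *Definitely*, first limb | not required | known toxicity | not required | not required |
| *Definitely*, second limb | required | required | required | no other reasonable explanation |
| *Probably* | required | required | required | other explanation unlikely |
| *Possibly* | required | required | not required | other causes may readily explain it |
| *Unrelated* | – | – | – | certainty of no relationship |

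The semicolon and *or* separate the first limb from the rest. The later conditions are relative clauses attached to *an event*, which is the second limb. Reading them as governing both limbs is possible but strained.

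**Case 1: effusion recorded as an adverse event five months after an injection, with OA a reasonable explanation.**
- *Definitely*, first limb: met by type of event (Section 4.3).
- *Definitely*, second limb: not met, because another reasonable explanation exists.
- *Probably*: not met if OA is a likely explanation.
- *Possibly*: met if five months is judged a reasonable sequence.
- *Unrelated*: not met unless the assessor is certain.

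The event can be graded *Definitely* and may also fit *Possibly*. No precedence rule is given.

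**Case 2: effusion two days after an injection, with no other cause apparent.**
- The second limb of *Definitely* and the *Probably* row both require confirmation by stopping or reducing the dose. This is hard to apply to a single injection already given (Section 7.4.1).
- *Possibly* presumes that other factors could readily have produced the event, which is not so here.
- Only the first limb of *Definitely* is left.

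Case 2 shows that the first limb is in practice the main route to the top grade, so its missing conditions are not a side issue. It also shows that the limb should be tightened rather than deleted.

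**Where the grade is used.** It feeds the tabulation of adverse reactions (Section 4.3) and the serious-and-related route (Section 10.1.1). It does not feed the primary analysis: the non-responder rule in Section 13 (Missing Data) turns on discontinuation for adverse events of the target knee, whatever their Table 2 grade.

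**The case against.** The case on the other side has real force, and several parts of it stand.

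- **Table 2 is a guideline.** It permits *Definitely* for a late OA event; it does not compel it. A reader might infer that every OA pain or effusion at any time counts as a device reaction. The text does not go that far, since *Possibly* remains open for the same event. But no other standard is given, so the ambiguity remains.
- **There are partial safeguards.** The adverse-event definition in Section 10 refers to a temporal association, and the cause is to be recorded when an event is judged unrelated. The definition gives no time window, however, and it decides what is an adverse event rather than what caused it. Section 4.3 describes the known reactions as transient and mild to moderate, but an OA flare can be both.
- **Ordinary recurrent OA pain may not be recorded as an adverse event.** Nothing says that it is, and the plan handles recurrence through Worst Knee Pain, the retreatment criteria and duration of response. A reader might infer that the device-related rate would largely measure the natural course of OA. That needs an assumption the documents do not supply.
- **No multiplier can be supported.** A reader might set assumed background events against true reactions. The synopsis gives 4 of 77 (5.2%) with device-related knee events over 4 weeks after a second injection. With 150 subjects, that rate per injection gives 150 × 0.052 = 7.8 reactions at one injection each, 450 × 0.052 = 23.4 at three, and 1,350 × 0.052 = 70.2 at the maximum of nine. An assumed 0.1 to 0.3 background events per subject-year over 150 × 3 = 450 subject-years (no dropout) gives 45 to 135. The ratio then runs from 45/70.2 = 0.6 to 135/7.8 = 17.3. The background rate has no anchor in the documents, and the ratio sets events over three years against reactions within 4 weeks of an injection.
- **Serious events are not lost.** They are documented whatever their cause (Section 10.1.1) and go to the IRB regardless of causality (Section 15.2). Over-grading mainly adds expedited reports.
- **The rewording alone may not change the related count.** The plan never says which grades count as related. A late event moved from *Definitely* to *Possibly* could still be treated as related, so the fix must settle that as well.

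**Conclusion.** The point holds as a defect in a stated rule: the highest causality grade can be reached with fewer conditions than the grades below it, and one event can fit two rows with no rule to choose between them. The overlap between the known reactions and OA symptoms makes this a practical problem in a single-arm study with a safety objective.

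The consequence is an unreliable tabulation by relationship and possible extra entries to the serious-and-related route. The number of events affected cannot be estimated from the documents. The primary endpoint, its test and the sample size are untouched. The conclusion rests on the natural grammar of the *Definitely* row and on at least some late knee events being recorded as adverse events.

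This should be corrected, but it does not threaten the trial's main conclusion.

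**What to change.** 1. Reword the *Definitely* row so that a known reaction to hylan G-F 20 qualifies only if it also follows a reasonable temporal sequence from the injection and is not explained by another reasonable hypothesis, such as the underlying OA or an injury. Do not simply extend the stopping-or-reducing condition to this limb, since it can hardly be met after a single injection.
2. State which row prevails when an event fits two.
3. State which grades count as related, both for the tabulation and for Section 10.1.1.
4. Tabulate target-knee adverse events by days since last injection. Start dates are already recorded (Section 8.1.13), and injection dates can be taken from the accountability records (Section 7.6).

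The cost is one reworded row, two added sentences and one derived variable, with no new data collection and no change to endpoints or sample size. The downside is that slightly more judgment is asked of the investigator.
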